### 3.2 Number of Subjects

We estimate that a total of 60 patients will be screened in-person for the study. We estimate that at least 18 patients will need to be enrolled given the high rate of drop outs seen in group psychotherapy studies in this population [114]. Patients who have been assigned to a group will be replaced only if they drop out prior to the first group therapy session (this avoids the possible symbolic message that if a subject were to die, that he would be easily replaced in the group). We aim for, at minimum, 8 subjects (two groups of at least 4 subjects each) will complete the study; at maximum, 36 subjects (six groups of six subjects each) will complete the study. (See Section 8.2.1 Sample Size and Power Estimate.)

### 3.3 Eligibility Criteria

Patients must have baseline evaluations performed prior to the first group therapy session and must satisfy all inclusion and exclusion criteria. In addition, the patient must be thoroughly informed about all aspects of the study, including the study visit schedule and required evaluations and all regulatory requirements for informed consent. The written informed consent must be obtained from the patient prior to enrollment. The following criteria apply to all patients enrolled onto the study unless otherwise specified.

#### 3.3.1 Inclusion Criteria

1. Gay-identified men  $\geq 50$  years old who are able to understand a written informed consent document and who are willing to sign it.
2. Laboratory confirmed HIV seropositive status; and diagnosed prior to 1996.
3. Moderate-to-severe demoralization, determined by a score of 8 or higher on the Demoralization Scale-II [27].

15. Insulin-dependent diabetes mellitus or poorly controlled non-insulin dependent diabetes mellitus (e.g., history of an episode of hypoglycemia or hospitalization for hyperglycemia on the current regimen).
16. Inadequate hepatic function (Total bilirubin > normal institutional limits, OR AST >3 upper institutional upper limit of normal, OR AST >3 upper institutional upper limit of normal), as determined by most recent laboratory tests.
17. Inadequate renal function as determined by eGFR < 30 mL/min/1.73 m^2 (based on the MDRD equation) or CrCl < 30 mL/min (based on the C-G equation).
18. Concomitant dosing of psilocybin with known UGT1A10 and UGT1A9 inhibitors (e.g., diclofenac and probenecid) will be avoided. There is *no* exclusion criterion based on the use of medications or substances that are inhibitors or inducers of CYP450 enzymes.
19. The use of efavirenz (a.k.a, Sustiva or Atripla).
20. If deemed by clinical judgment of the study investigators to be unsafe for undergoing the intervention and/or inappropriate for participating in a therapy group.

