## Abbreviations

AGPA	American Group Psychotherapy Association
AHP	Alliance Health Project
AIDS	Acquired Immune Deficiency Syndrome
Albumin	Alb
AlkPhos	Alkaline phosphatase
Alt	Alanine aminotransferase
AMAS	Antiretroviral Medication Adherence Scale
AMAS	ART Medication Adherence Scale
ANOVA	Analysis of Variance
ART	Antiretroviral Therapy
Ast	Aspartate aminotransferase
AUDIT	Alcohol Use Disorders Identification Test
BUN	Blood Urine Nitrogen
CBC	Complete Blood Count
ChEQ	Challenging Experience Questionnaire
CrEQ	Credibility/Expectancy Questionnaire
CESD-R	Centers for Epidemiologic Studies Depression Scale—Revised
CHR	Committee on Human Research
CMP	Comprehensive Metabolic Panel
CORF	Community Observer Rating Form
Cr	Creatinine
CSS	Client Satisfaction Scale
C-SSRS	Columbia Suicide Severity Rating Scale
CTC	Concomitant Therapeutics Checklist
DEA	Drug Enforcement Agency
DS-II	Demoralization Scale—II
DSM	Data and Safety Monitor
DUDIT	Drug Use Disorders Identification Test
DUFSS-5	Duke UNC Functional Social Support Questionnaire-5
ECG	Electrocardiogram
ECR-M16	Experiences in Close Relationships scale—Modified 16
ES	Effect Size
FDA	Food and Drug Administration
FT4	Free thyroxine
Gluc	Glucose
GPIRS	Group Psychotherapy Intervention Rating Scale
GQ	Group Questionnaire
HAART	Highly Active Antiretroviral Therapy
HANA	HIV-Associated Non-AIDS
HARSI	HIV and Abuse Related Shame Inventory
Hct	Hematocrit
Hgb	Hemoglobin
HIM	Hill Interaction Matrix
HIPPA	Health Insurance Portability and Accountability Act
HIV	Human Immunodeficiency Virus
ICC	Intraclass Correlation Coefficient
ICF	Informed Consent Form
ICG	Inventory of Complicated Grief
IND	Investigational New Drug
IOS	Inclusion of Other in the Self
IPA	Interpretive Phenomenological Analysis
IPIP-OE-20	International Personality Item Pool—Openness to Experience-20
LPPI	Langley Porter Psychiatric Institute
LSD	Lysergic acid diethylamide-25

[figure not shown]
---

LTAS	Long-term AIDS Survivor
MAIA	Multidimensional Assessment of Interoceptive Awareness
MAOI	Monoamine Oxidase Inhibitors
MEQ-30	Mystical Experience Questionnaire—30
MOCA	Montreal Cognitive Assessment
MQoL-RS	McGill Quality of Life Questionnaire—Revised-Short
NR	Nature Relatedness Scale, Short Form
NEO-PI-R	Revised NEO Personality Inventory
OPLH	Older People Living with HIV
PA-SEGT	Psilocybin-assisted Supportive-Expressive Group Therapy
PCL-5	PTSD Checklist
PEQ-S	Persisting Effects Questionnaire—Spirituality
PLH	People Living with HIV
Plt	Platelet

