##### Metabolism

After ingestion, psilocybin is rapidly dephosphorylated to psilocin, which is metabolized via oxidation and glucuronidation in the small intestine and the liver, and subsequently excreted renally [91, 93, 94].

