### 6.4 Schedule of Procedures and Observations

The study-specific assessments are detailed in this section and outlined in [Section 6 Schedule of Study Procedures and Assessments](#). Screening assessments will be performed on enrollment. Any results falling outside of the reference ranges may be repeated at the discretion of the investigator. All on-study visit procedures are allowed a window of  $\pm 7$  days unless otherwise noted. Treatment or visit delays for public holidays or weather conditions do not constitute a protocol violation.

A written, signed, informed consent form (ICF) and a Health Insurance Portability and Accountability Act (HIPAA) authorization must be obtained before any study-specific assessments are initiated. A copy of the signed ICF will be given to the subject and a copy will be filed in the medical record. The original will be kept on file with the study records.

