## 6.4.2 In-person Screening and Enrollment

Screening procedures and assessments to be completed on day of Enrollment (prior laboratory results from UCSF clinics may be considered instead of performing labs at enrollment if the results are less than 6 months old):

- Demographics questionnaire (Age, ethnicity/race, civil status, years of education, income)
- Vital signs; Physical examination; Complete medical and psychiatric history, including current medication list; Performance status (PPSV2); Mental Status Exam; Cognitive Status (Montreal Cognitive Assessment)
- Complete blood count (WBC, Hgb, Hct, Plt)
- Comprehensive metabolic panel (Na, K, Cl, CO2, BUN, Cr, Gluc, Tbili, Ast, Alt, AlkPhos, TProt, Alb)
- TSH, FT4
- Urinalysis
- Urine toxicology (must be completed on day of Enrollment)
- HIV viral load, CD4 count, CD8 count
- RPR or Treponemal Antibody
- Electrocardiogram (ECG)
- Selected screening portions of Structured Clinical Interview for DSM-5 Clinical Trials Version (SCID-5); sections on current Depressive disorders; lifetime Psychotic disorders, Bipolar disorders and Hallucinogen-related disorders), Structured Clinical Interview for DSM-5 Personality Disorders, self-report version (SCID-5-PD; section on Cluster B disorders)
- Columbia Suicide Severity Rating Scale (C-SSRS): Baseline/Screening (last 12 months)
- ART Medication Adherence Scale (AMAS), Centers for Epidemiologic Studies Depression Scale—Revised (CESD-R), Demoralization Scale—II (DS-II), Inventory of Complicated Grief (ICG), McGill Quality of Life Questionnaire-Revised-Short (MQoL-RS), PTSD Checklist-5 (PCL-5), Schedule of Attitudes towards Hastened Death (SAHD), State-Trait Anxiety Inventory (STAI).

Upon completing a successful in-person screening, subjects will also meet individually with one of the study therapists for 30 minutes to develop rapport and to discuss details about the subject's personal life, such as past and current relationships, family dynamics, and concerns about their disease. Finally, the subject will be placed on the waitlist until 6 subjects are available to start a group.

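### Exclusion criterion 16 states its AST limit twice and sets none for ALT, so an isolated ALT rise is not automatically excluded

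*Combined protocol and SAP*

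**What the plan says.** Section 3.3.2, item 16, excludes men with inadequate hepatic function, judged on their most recent laboratory tests. It has three limbs joined by OR. The first is total bilirubin above normal institutional limits. The other two read "OR AST >3 upper institutional upper limit of normal, OR AST >3 upper institutional upper limit of normal".

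Section 3.3 makes the criteria binding: a patient "must satisfy all inclusion and exclusion criteria".

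The protocol treats ALT as a test distinct from AST. The Abbreviations list gives it its own entry, "Alanine aminotransferase", and the metabolic panel in Section 6.4.2 names both enzymes: "Gluc, Tbili, Ast, Alt, AlkPhos, TProt, Alb".

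Three other provisions bear on the point:

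- Section 3.3.2, item 20, is a discretionary exclusion: "If deemed by clinical judgment of the study investigators to be unsafe for undergoing the intervention". It gives no laboratory threshold.
- Section 6.4 says of screening: "Any results falling outside of the reference ranges may be repeated at the discretion of the investigator".
- Section 6.4.2 allows older results to stand in: "prior laboratory results from UCSF clinics may be considered instead of performing labs at enrollment if the results are less than 6 months old". The assessment schedule at the end of the document shows laboratory tests once, at enrollment.

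**The concern.** Two identical conditions joined by OR are one condition, so the third limb of item 16 can never exclude anyone. The protocol measures two transaminases and sets a limit for only one. Because the criteria bind as written, a man with a marked rise in ALT alone is not caught by the rule meant to define inadequate hepatic function.

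The documents give some reason to care about that rule. Section 4.1.1 (Metabolism) says psilocin is "metabolized via oxidation and glucuronidation in the small intestine and the liver". Item 18 of the same exclusion list avoids inhibitors of two glucuronidating enzymes, so the protocol itself treats this pathway as relevant to safety. Section 1.1 describes people living with HIV as at increased risk of serious liver disease. Safety is also part of the primary objective (Section 2.1.1).

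What is at stake is consistent screening. One screener may read the repeated limb as ALT and exclude; another may apply the text and enroll. The Data and Safety Monitor audits conduct against the protocol (Section 9.7), and an exclusion under item 16 for ALT alone would have no basis in the text.

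**Working it through.** The plan gives no figure to reproduce, so the check is textual and logical.

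**Step 1: look for ALT in the eligibility rules.** It is in none of the 3 inclusion criteria (Section 3.3.1) and none of the 20 exclusion criteria (Section 3.3.2). It appears in the Abbreviations list and in the Section 6.4.2 panel. No other section supplies a limit for it.

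**Step 2: reduce item 16 to its logic.** Let B = bilirubin above normal, A = AST above 3 × ULN, L = ALT above 3 × ULN, each yes (1) or no (0). The multiplication sign is absent from the text supplied; that may be lost in extraction, and nothing here depends on it.

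- As written: B or A or A, which equals B or A.
- With ALT in the third limb: B or A or L.

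**Step 3: count the result patterns.** Three yes/no tests give 2³ = 8 patterns.

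| Rule | Patterns not excluded | Patterns excluded |
|---|---|---|
| As written | B = 0, A = 0, L = 0 or 1 (2 patterns) | 8 − 2 = 6 |
| ALT in third limb | B = A = L = 0 (1 pattern) | 8 − 1 = 7 |

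The rules differ in one pattern: B = 0, A = 0, L = 1, which is ALT raised alone. These counts describe the logic of the rule and are not frequencies. They do not mean that one man in eight is affected.

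**Step 4: an illustration.** Take a candidate with normal bilirubin, AST of 2 × ULN and ALT of 6 × ULN (values assumed for the example, not taken from the documents). He does not meet item 16 as written. With ALT in the third limb he is excluded.

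**Step 5: what else could stop him.** Item 20 could, if an investigator judged him unsafe. The repeat-test provision in Section 6.4 permits a second measurement but does not say what follows from it. No further laboratory test is scheduled after enrollment.

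**Step 6: how many men.** Section 3.2 expects about 60 men to be screened in person. The documents give no rate of isolated ALT elevation, so the number affected cannot be estimated.

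**The case against.** The strongest reply is that this is a typing error with little consequence. Nothing suggests that anyone chose to leave ALT out, and a clinician would probably read the repeated limb as ALT. The result is in front of the study team at enrollment, together with a physical examination and a full history. Item 20 is itself a numbered criterion and allows exclusion. The bilirubin limb is strict, since any value above normal excludes. Each man receives one dose, Section 5.1 describes the drug as not physiologically toxic at the doses used, and the side effects listed in Section 4.1.1 include nothing hepatic. No endpoint, sample size or analysis changes.

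Most of this stands, and it limits the weight of the point. It does not remove the defect. The protocol chose explicit hepatic thresholds over judgment alone, and for one transaminase the threshold is absent. A reading that depends on each screener silently correcting the text is not a rule.

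A second reply is that the timing of the laboratory tests is beside the point. That is largely right. The man in question already has a known ALT, a later test would not trigger item 16 either, and the six-month allowance applies equally to bilirubin and AST. The single scheduled measurement means only that no later planned liver result would prompt a second look.

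A third reply is that AST and ALT differ by one letter, and the text was machine-read. One-letter discrepancies do occur in it: Section 8.5.1 prints QPIRS for the scale called GPIRS elsewhere. A misread letter cannot be ruled out from the text alone. Both limbs repeat the same awkward phrasing, which suggests copying by the author, but a look at the source document would settle it.

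**Conclusion.** The concern holds. Item 16 as printed is a bilirubin-or-AST rule. ALT, though measured at screening, is in no numbered criterion, and ALT above 3 × ULN with normal bilirubin and AST at or below 3 × ULN is excluded only if an investigator chooses to invoke item 20.

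The size is one result pattern out of eight, with an unknown number of men behind it. The fault lies in the consistency of a safety rule; no harm has been shown and no statistical result depends on it. Two assumptions remain. That ALT was intended is an inference from the duplicated threshold and from a panel that measures both enzymes. That the source document prints AST twice should be confirmed. The point should be corrected, but it is modest.

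**What to change.** After checking the source document and confirming that ALT was intended, amend the repeated limb so that item 16 reads: *Total bilirubin above the institutional upper limit of normal, OR AST >3 × institutional ULN, OR ALT >3 × institutional ULN*. This also states the multiple explicitly.

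The change is a one-line amendment using a test already in the screening panel, with no added visit or procedure. Its possible cost is a few more screen failures, a number the documents do not allow to be estimated. If the sponsor did mean to leave ALT out, the duplicate limb should be deleted and the reason stated.

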### 3.4 Duration of Therapy

In the absence of treatment delays due to adverse events, treatment may continue for 8 weeks or until:

- Inter-current illness that prevents further administration of treatment
- Unacceptable adverse event(s)

---

 Individuals taking antidepressants, anxiolytics and stimulants will be presented with the option of tapering off, and remaining off, of their medication for the duration of the study, if their prescribing physician agrees with this course of treatment.

- Patients decides to withdraw from the study
- Significant patient non-compliance with protocol
- General or specific changes in the patients' condition render the patient unacceptable for further treatment in the judgment of the investigator.

### **3.5 Duration of Follow Up**

Patients will be followed for 3 months after completion of treatment or removal from study, or until death, whichever occurs first. Patients removed from study for unacceptable treatment related adverse event(s) will be followed until resolution or stabilization of all treatment related adverse events.

### **3.6 Randomization Procedures**

Patients will not be randomized; this is an open-label pilot trial with one treatment arm.

### **3.7 Study Timeline**

#### **3.7.1 Primary Completion**

The study will reach primary completion 36 months from the time the study opens to accrual.

#### **3.7.2 Study Completion**

The study will reach study completion 48 months from the time the study opens to accrual.

## 4 Study Drugs

### 4.1 Description, Supply and Storage of Investigational Drugs

#### 4.1.1 Investigational Drug: Psilocybin

Psilocybin is available as a powder that can be encapsulated for oral administration.

##### Classification

Psilocybin is an indoleamine psychedelic and is one of the “classic psychedelics.” It has a chemical structure similar to that of the neurotransmitter serotonin.

##### Mechanism of Action

Psilocybin is an agonist of serotonin 5HT2A, 2C and 1A receptors [92, 101].

##### Metabolism

After ingestion, psilocybin is rapidly dephosphorylated to psilocin, which is metabolized via oxidation and glucuronidation in the small intestine and the liver, and subsequently excreted renally [91, 93, 94].

##### Contraindications

Current safety standards for experimental psilocybin administration [24, 143] include providing a comfortable environment, the presence of supportive and non-directive therapists or research staff, and strict exclusion criteria. Beyond this basic principle, psilocybin should generally not be administered to individuals with a personal or family history of psychosis or bipolar disease, or individuals who are acutely suicidal. It should also not be administered to individuals with severe cardiovascular disease or CNS disease (metastases, a seizure disorder, or traumatic brain injury). Co-administration with medications associated with the serotonin syndrome [144] should be avoided.

##### Availability

Psilocybin is a Schedule I compound, and so requires a DEA Schedule I license to handle. For the purposes of this study, psilocybin is available from the laboratory of [name] at Johns Hopkins University (IND#133202).

##### Storage and handling

Psilocybin is stored at 15-30°C. Each subject's dose will be, to the nearest milligram, as close as possible to that indicated by their actual bodyweight (e.g., 0.30mg/kg or 0.36mg/kg), with a maximum dose not to exceed that calculated for a BMI of 35 at that participant's height. The psilocybin will be provided to UCSF in powder form, and the UCSF Investigational Drug Service of the UCSF Department of Pharmacy Services will encapsulate the drug. The study drug will be stored in a secure vault in the Investigational Drug Service in the Inpatient Pharmacy in Moffitt-Long Hospital ([name]).

##### Side Effects

Psilocybin is known to be physiologically safe at the doses proposed for this study, and is not addictive [92, 102]. Safe administration is dependent on using a supportive and structured administration protocol [24]. Psilocybin is known to possibly cause the following transient side effects: Anxiety, thought disorder, nausea, emesis, increase or decrease in heart rate, increase or decrease in blood pressure, and headache [18, 24, 91, 95, 145, 146]. Anxiety and thought disorder reactions appear to be dose-dependent, with higher doses associated with greater frequency of temporary anxiety and thought disorder reactions [138].

### Clinical Safety Data

Psilocybin, in the form of psilocybe mushrooms, has been consumed by humans for ritual and healing purposes for at least hundreds of years [147]. The most extensive review of mid-Century reports of the safety of the controlled, clinical uses of psychedelics, including psilocybin, found an overall low incidence of adverse events [103]. After clinical research with psilocybin in North America stopped in the 1970s, psilocybin continued to be used legally as a psychotherapy adjunct in Germany and Switzerland in the 1980s and 90s, but no comprehensive safety data are available from this period [104, 148].

Since the 1990s, hundreds of doses of psilocybin have been administered to humans in clinical trials and research laboratories across North America and Europe. Gouzoulis-Mayfrank et al found negligible acute effects on vital signs (heart rate, blood pressure, temperature) and neuroendocrine levels (cortisol, prolactin, growth hormone), but did find significant transient mental status changes in eight healthy volunteers administered a moderate dose (0.2mg/kg, with total dose <15mg) of oral psilocybin [149]. A review of results from the Vollenweider laboratory in Zurich, Switzerland found that in 110 subjects administered 1-4 low-to-high doses of oral psilocybin there were no detectable persisting adverse effects, and all acute adverse reactions (e.g., dysphoria or anxiety) were controlled with interpersonal support alone, meaning no pharmacologic or other medical interventions were necessary [143]. Moreover, several subjects who did report acutely distressful experiences later claimed in long-term follow up that these experiences had been “enriching”. [143] A subsequent review from that laboratory found that among 261 subjects who received low-to-high doses of oral psilocybin, both mystical-type experiences and acute anxious reactions were strongly positively correlated with drug dose [150]. Importantly, anxious reactions were also strongly correlated with the experimental setting (more anxiety was reported if the subject underwent a PET scan during the experiment), which argues in favor of the idea that the risk of adverse events can be mitigated by providing a comfortable and supportive setting for drug administration. This laboratory’s recent findings from 50 subjects [151], and another 25 subjects [152] receiving a moderate oral dose of psilocybin (0.16mg/kg po or 0.215mg/kg po) reported no adverse events, and found improvement in mood. In contrast to the PET study above, another laboratory in London found no adverse events when they administered moderate dose iv psilocybin to 15 healthy subjects with prior psychedelic experience while undergoing brain fMRI; these subjects reported improved well-being on 2-week follow up [141].

to-high doses of oral psilocybin, the only adverse event reported was transient hypertension [110]. Of 15 nicotine-dependent smokers receiving moderate-to-high doses of oral psilocybin, adverse events included acute anxiety, mild transient increases in hypertension and heart rate, and mild headaches [108]. Of 10 subjects with alcohol dependence administered moderate-to-high doses of oral psilocybin, the only adverse event reported was mild transient hypertension [107]. A recent open-label pilot study of 12 subjects with treatment-resistant depression, each receiving a low oral dose (10mg) followed one week later by a high dose (25mg) found transient anxiety, thought disorder, nausea and headache, but no severe or unexpected adverse events when followed for up to 3 months after the high dose session [153]. Finally, recent epidemiological data argue for a positive correlation between lifetime classic psychedelic use (including psilocybin) in the US population and reduced rates of past month psychological distress, past year suicidal ideation and past year suicidal attempt [154].

